xxxxxx	xxxxxx	xxxxxxxxxx	ddmmyyyy / hh:mm (xx)	ddmmyyyy / hh:mm (xx)	Yes / No	xxxxxx	xxx xxx	xxx / xxx	P / C

[1] WHO Drug Global Version 2019;3, September 1, 2019. L2: The second level of Anatomical Therapeutic Chemical (ATC) classification.

[2] OD = Once a day, BP = Twice a day, PRN = As needed, TDS = Three times a day, QDS = Four times a day.

[3] PO = Oral, TOP = topical, PRN = Take as needed.

[4] P=Prior to vaccine, C=Concomitant with vaccine.

If the medication stop date is before the vaccination date, the medication will be assigned as being prior to vaccine. In all other cases, the medication is assigned as being concomitant with vaccine treatment.

* = Estimated date/time

Programming Notes: concatenate * to end of start and/or stop date if they are estimated.
update footnotes 2 and 3 to reflect codes used in actual data

Listing 16.2.5
Vaccination Administration

Cohort	Participant	Vaccine administered?	Date/time administered	If no, reason not done		Time removed from freezer	Batch number / Expiry Date	Dose given	Location	First Participant	Observed for required time [1]
				hh:mm	ddmmmyyy hh:mm						
xxxxxx	xxxxxx	Yes/No	xxxxxx	hh:mm	ddmmmyyy hh:mm	xxxxxx	xxxxxx/ ddmmmyyy	xxxxx / xxxx	xxxxxx	Yes/No	Yes/No

[1] The required time is 60 minutes for the first participant of each cohort and 30 minutes for all others.

Listing 16.2.6.1.1

Local and Systemic Reactions

Cohort	Participant	Vaccination Date / Time (Study Day)		Reaction	Day 0 Pre		Day 0 Post		Day 1		Day 2		Day 3	
		ddmmyy	hh:mm (xx)		ddmmyy	hh:mm	xx.x	xx.x	xx.x	xx.x	xx.x	xx.x	xx.x	xx.x
xxxxxx	xxxxxx	ddmmyy	/	Date	ddmmyy	hh:mm	xx.x	yes/no	xx.x	yes/no	xx.x	xx.x	xx.x	xx.x
				Time	ddmmyy	xx.x	yes/no	xx.x	xx.x	yes/no	xx.x	xx.x	xx.x	xx.x
				Injection site swelling	ddmmyy	xx.x	yes/no	xx.x	xx.x	yes/no	xx.x	xx.x	xx.x	xx.x
				Size of swelling (mm)	ddmmyy	xx.x	yes/no	xx.x	xx.x	yes/no	xx.x	xx.x	xx.x	xx.x
				Injection site redness	ddmmyy	xx.x	yes/no	xx.x	xx.x	yes/no	xx.x	xx.x	xx.x	xx.x
				Size of redness (mm)	ddmmyy	xx.x	yes/no	xx.x	xx.x	yes/no	xx.x	xx.x	xx.x	xx.x
				Pain (at injection site)	ddmmyy	xx.x	yes/no	xx.x	xx.x	yes/no	xx.x	xx.x	xx.x	xx.x
				Warmth (at injection site)	ddmmyy	xx.x	yes/no	xx.x	xx.x	yes/no	xx.x	xx.x	xx.x	xx.x
				Muscle ache	ddmmyy	xx.x	yes/no	xx.x	xx.x	yes/no	xx.x	xx.x	xx.x	xx.x
				Tiredness	ddmmyy	xx.x	yes/no	xx.x	xx.x	yes/no	xx.x	xx.x	xx.x	xx.x
				Headache	ddmmyy	xx.x	yes/no	xx.x	xx.x	yes/no	xx.x	xx.x	xx.x	xx.x
				Nausea	ddmmyy	xx.x	yes/no	xx.x	xx.x	yes/no	xx.x	xx.x	xx.x	xx.x
				Feverishness	ddmmyy	xx.x	yes/no	xx.x	xx.x	yes/no	xx.x	xx.x	xx.x	xx.x
				Chills	ddmmyy	xx.x	yes/no	xx.x	xx.x	yes/no	xx.x	xx.x	xx.x	xx.x
				Joint ache	ddmmyy	xx.x	yes/no	xx.x	xx.x	yes/no	xx.x	xx.x	xx.x	xx.x
				Generally feeling unwell	ddmmyy	xx.x	yes/no	xx.x	xx.x	yes/no	xx.x	xx.x	xx.x	xx.x
				Medication Taken	ddmmyy	xx.x	yes/no	xx.x	xx.x	yes/no	xx.x	xx.x	xx.x	xx.x
				Visit to A&E	ddmmyy	xx.x	yes/no	xx.x	xx.x	yes/no	xx.x	xx.x	xx.x	xx.x

* = indicates worst post-baseline incidence/highest value
All local and systemic reactions recorded on Day 0 (pre and post) are as recorded by the investigator. The reactions recorded Day 1 to day 3 are recorded by the participant in a diary card.

Severity: 0 = None, 1 = No interference with daily activities, 2 = Some interference with daily activities, 3 = Significant interference with daily activities, 4 = ER visit or hospitalization.
Medication Taken and Visit to A&E are yes if these were recorded as such for any symptom at the specific timepoint.

Programming note: place a "*" against the worst post-baseline incidence/highest value for each reaction for each participant, in the event of a tie the first one should be flagged. If all 0 then none should be flagged
Programming note: The numeric grade should be displayed in the listing

Listing 16.2.6.1.2
Diary Card: Medications Taken

Cohort	Participant	Study Day	Date/time	Symptom(s)	Medication Taken	Medication Name	Dose taken (units)	Number of times taken	Additional symptoms this medication refers to
xxxxxx	xxxxxx	0/1/2/3	ddmmmyyy hh:mm	xxxxxx	xxxxxx	xxxxxx	xxxx	xx	xxxxx

Programming Note: Only display details for the days on which medication was taken. If no medication taken throughout then this listing will be empty
Programming Note: Symptoms should list all of the symptoms that this medication was listed against on the specific day it was taken.

Listing 16.2.6.2
HBV Disease Markers

Cohort	Participant	Visit	Date/time	Parameter	Result	Comments
xxxxxx	xxxxxx	Day x	ddmmyyy / hh:mm	HBV DNA HBV pRNA Hepatitis B surface Antibody Hepatitis B surface Antigen Hepatitis B core Antibody Hepatitis B core Antigen Hepatitis B e Antibody Hepatitis B e Antigen		

Multi-parameter index
HBeAg loss
HBsAg Loss
HbeAg and HBsAg seroconversion

Programming Note: The parameters will not be available for all participants at all visits. For healthy participants we should only expect hepatitis B surface antigen, hepatitis B surface antibody and hepatitis B core antibody.

Listing 16.2.6.3
ELISpot

Cohort	Participant	Visit	Date	Lab Test	Sample	IFNG SFC/10 ⁶ PBMC Background Corrected
xxxxxx	xxxxxx	Day x	ddmmYYYY	Genotype C/ Control	xxx	xx

Cohort	Participant	Visit	Date	Lab Test	Stimulating Condition	Sample	Result
xxxxxx	xxxxxx	Day x	ddmmYYYY	Genotype C/ Genotype D	xxxxx	%CD4_CD154 %CD4_IFNG %CD4_IFNG+IL2 %CD4_IFNG+TNFa %CD4_IFNG+TNFa+ IL2 %CD4_IL2 %CD4_IL2+TNFa %CD4_TNFa %CD8_CD107a %CD8_IFNG %CD8_IFNG+IL2 %CD8_IFNG+TNFa %CD8_IFNG+TNFa+ IL2 %CD8_IL2 %CD8_IL2+TNFa %CD8_TNFa CD4_CD107a_MFI CD4_IFNG_MFI CD4_IL2_MFI CD4_TNFa_MFI CD8_CD107a_MFI CD8_IFNG_MFI CD8_IL2_MFI CD8_TNFa_MFI	xxx

Listing 16.2.6.5
Neutralising Antibody Sample Collection

Cohort	Participant	Visit	Date	Time
xxxxxx	xxxxxx	Day x	ddmmyyy	

Listing 16.2.7 Adverse Events						
Cohort/ Participant	Adverse Event (verbatim) Preferred Term / MedDRA SOC [1]	Start Date (study day) / Stop Date (study day)	Severity [2]	TE [3] / Serious	Special Interest / Related to Study Drug	Outcome Treatments Provided
xxxxxx / xxxxx	xxxxxxxxx / xxxxxxxx / xxxxxx	ddmmmyyy (xx) / ddmmmyyy (xx)	Grade 1/ Grade 2/ Grade 3/ Grade 4	Yes/No Yes/No	Yes/No Yes/No	xxxxxxxxxxxx

[1] MedDRA Version 22.1.

[2] Event Severity: Grade 1 = Mild, Grade 2 = Moderate, Grade 3 = Severe, Grade 4 = Life Threatening and Grade 5 = Death.

[3] TE = Treatment Emergent. An event is considered vaccine-emergent if the start date of the adverse event is on or after vaccination.

Programming note(s):

Only participants with AEs will be shown in this listing.

Listing 16.2.8.1
Haematology

Parameter	Cohort	Participant	Study Day	Date	Standard Result	Unit	Range		Clin. Sig.	Flag	Toxicity Criteria	Toxicity Grade
							Low	High				
xxxx	xxxxxx	xxxxxx	xxxx	ddmmyy/yy	xx.x	xx	xx.x	xx.x	xx.x	○	Yes/N	H/L

= Baseline grade.
* = Maximum post-baseline grade.

Programming Note(s) :

List by parameter first, then subject and then day/date.
If more than one Toxicity criteria apply to a laboratory parameter (e.g. hyper and hypo) then list them all.
Include all data collected, including any unscheduled data.
If there is a tie for the maximum post-baseline result then all should be flagged.

Repeat for the following listing:
16.2.8.2 Chemistry (including Liver Function Tests).

Listing 16.2.8.3
Urinalysis

Parameter	Cohort	Participant	Study Day	Date	Original Result	Unit	Standard Result	Unit	Toxicity Criteria	Toxicity Grade
xxxxxx	xxxxxx	xxxx	xxxx	ddmmYYYY						

Listing 16.2.8.4						
Cohort	Participant	Visit	Date/time	HIV Antibody	HCV Antibody	HDV Antibody
xxxxxx	xxxxxx	xxx	ddmmyyy hh:mm	Detected/Not Detected	Detected/Not Detected	Detected/Not Detected

Listing 16.2.8.5 Urine Pregnancy Test					
Cohort	Participant	Visit	Date	Result	Comments
xxxxxx	xxxxxx	xxxx	ddmmyyy	Positive / Negative	xxxxxxxxxxxxxxxx

Listing 16.2.9
Vital Signs

Parameter	Cohort	Participant	Visit	Date	Time Started Sitting	Collection Time	Result	Unit	Toxicity Criteria	Toxicity Grade
Temperature	xxxxxx	xxxxxx	xxxx	ddmmyyy	hh:mm	hh:mm	xx.xx	xx	xxx	x

= Baseline grade.
* = Maximum post-baseline grade.

Programming Note(s) :

List by parameter first, then subject and then day/date.
If more than one Toxicity criteria apply to a laboratory parameter (e.g. hyper and hypo) then list them all.
Include all data collected, including any unscheduled data.
If there is a tie for the maximum post-baseline result then all should be flagged.

Listing 16.2.10
Physical Examination

Cohort	Participant	Visit	Date	Body System	Finding	Comments
xxxxxx	xxxxxx	xxxx	ddmmmyyy	Skin Respiratory Cardiovascular Abdominal Lymphatic	Normal / Abnormal / Abnormal / Not Done	Not Clinically Significant / Clinically Significant / xxxxxx

A complete physical examination was performed at screening and Day 0 (prior to vaccination). Directed physical examinations were performed as required at each follow-up visits

Programming note(s):

Include complete and directed physical examinations.

Only body systems reported are included for directed physical examinations.

Listing 16.2.11
Visit Dates

Cohort	Participant	Visit	Date	Source of Unscheduled Visit	Reason for unscheduled visit	Comments
xxxxxx	xxxxxx	xxxx	ddmmyyy	xxxxxxxxxx		xxxxxxxxxxxx

Listing 16.2.12 Covid-19 Vaccination						
Cohort	Participant	Vaccination Type(1 and 2)	Date of Vaccination 1	Date of Vaccination 2	Vaccination Type (3)	Date of Vaccination 3
xxxxxx	xxxxxx	xxxx	ddmmyyy	ddmmyyy	xxxx	ddmmyyy

15.APPENDICES

15.1. Appendix 1: Toxicity Grade Criteria for Lab Parameters

Table 2: Toxicity Grade Criteria for Values Below Normal Range (Chemistry)

Analyte	LOW			
	1	2	3	4
Sodium (Hyponatremia)	132-134	130-131	125-129	<125
Potassium (Hypokalemia)	3.5-3.6	3.3-3.4	3.1-3.2	<3.1
Albumin (Hypoalbuminemia)	2.8-3.1	2.5-2.7	<2.5	N/A
Glucose (Hypoglycemia)	65-69	55-64	45-54	<45

Table 3: Toxicity Grade Criteria for Values Above Normal Range (Chemistry)

Analyte	HIGH			
	1	2	3	4
Sodium (Hypernatremia)	144-145	146-147	148-150	>150
Potassium (Hyperkalemia)	5.1-5.2	5.3-5.4	5.5-5.6	>5.6
BUN	23-26	27-31	>31	
Creatinine	1.5-1.7	1.8-2.0	2.1-2.5	>2.5
Total Bilirubin if normal ASL-AST	1.1-1.5*ULN	1.6-2.0*ULN	2.0-3.0*ULN	>3.0*ULN
Total Bilirubin if AST/ ALT elevated	1.1-1.25*ULN	1.26-1.5*ULN	1.51-1.75*ULN	>1.75*ULN
ALP	1.1-2.0*ULN	2.1-3.0*ULN	3.1-10*ULN	>10*ULN
AST	1.1-2.5*ULN	2.6-5.0*ULN	5.1-10*ULN	>10*ULN
ALT	1.1-2.5*ULN	2.6-5.0*ULN	5.1-10*ULN	>10*ULN

Table 4: Toxicity Grade Criteria for Values Below Normal Range (Haematology)

Analyte	LOW			
	1	2	3	4
Haemoglobin (Female)	11.0-12.0	9.5-10.9	8.0-9.4	<8.0
Haemoglobin (Male)	12.5-13.5	10.5-12.4	8.5-10.4	<8.5
Platelets	125-140	100-124	25-99	<25
WBC	2.5-3.5	1.5-2.49	1.0-1.49	<1.0
Neutrophils	1.5-2.0	1.0-1.49	0.5-0.99	<0.5
Lymphocytes	0.75-1.0	0.74-0.5	0.25-0.49	<0.25

Table 5: Toxicity Grade Criteria for Values Above Normal Range (Haematology)

Analyte	HIGH			
	1	2	3	4
WBC	10.8-15.0	15.1-20.0	20.1-25.0	>25.0
Eosinophils	0.6-1.5	1.51-5.0	>5.0	N/A

Table 6: Toxicity Grade Criteria for Values Outside Normal Range (Coagulation)

Analyte	LOW			
	1	2	3	4
Prothrombin time	1.0-1.10*ULN	1.11-1.20*ULN	1.21-1.25*ULN	>1.25*ULN
PTT	1.0-1.2*ULN	1.21-1.4*ULN	1.41-1.5*ULN	>1.5*ULN
Fibrinogen (above normal)	150-200	125-149	100-124	<100
Fibrinogen (below normal)	400-500	501-600	>600	N/A

Table 7: Toxicity Grade Criteria for Values Outside Normal Range (Urinalysis)

Analyte	LOW			
	1	2	3	4
Protein	Trace	1+	2+	Hospitalisation or dialysis
Glucose	Trace	1+	2+	Hospitalisation or hyperglycaemia

15.2. Appendix 2: Toxicity Grade Criteria For Vital Signs

Table 8: Toxicity Grade Criteria for Vital Signs

Vital Signs	Mild (Grade 1)	Moderate (Grade 2)	Severe (Grade 3)	Potentially Life-threatening (Grade 4)
Fever (°C) (°F)	38.0 – 38.4 100.4 – 101.1	38.5 – 38.9 101.2 – 102.0	39.0 – 40 102.1 – 104	> 40 > 104
Tachycardia – beats per minute	101 – 115	116 – 130	> 130	ER visit or hospitalization for arrhythmia
Bradycardia – beats per minute	50 – 54	45 – 49	< 45	ER visit or hospitalization for arrhythmia
Hypertension (systolic) – mm Hg	141 – 150	151 – 155	> 155	ER visit or hospitalization for malignant hypertension
Hypertension (diastolic) – mm Hg	91 – 95	96 – 100	> 100	ER visit or hospitalization for malignant hypertension
Hypotension (systolic) – mm Hg	85 – 89	80 – 84	< 80	ER visit or hospitalization for hypotensive shock
Respiratory Rate – breaths per minute	17 – 20	21 – 25	> 25	Intubation

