Tenderness	Mild discomfort to touch	Discomfort with movement	Significant discomfort at rest	ER visit or hospitalization
Erythema/Redness *	2.5 – 5 cm	5.1 – 10 cm	> 10 cm	Necrosis or exfoliative dermatitis
Induration/Swelling **	2.5 – 5 cm and does not interfere with activity	5.1 – 10 cm or interferes with activity	> 10 cm or prevents daily activity	Necrosis

* In addition to grading the measured local reaction at the greatest single diameter, the measurement should be recorded as a continuous variable.

** Induration/Swelling should be evaluated and graded using the functional scale as well as the actual measurement.

Contains Nonbinding Recommendations

Vital Signs *	Mild (Grade 1)	Moderate(Grade 2)	Severe (Grade 3)	Potentially Life Threatening (Grade 4)
Febrile (°C) **	38.0 – 38.4	38.5 – 38.9	39.0 – 40	> 40
	100.4 – 101.1	101.2 – 102.0	102.1 – 104	> 104
Tachycardia - beats per minute	101 – 115	116 – 130	> 130	ER visit or hospitalization for arrhythmia
Bradycardia - beats per minute***	50 – 54	45 – 49	< 45	ER visit or hospitalization for arrhythmia
Hypertension (systolic) - mm Hg	141 – 150	151 – 155	> 155	ER visit or hospitalization for malignant hypertension
Hypertension (diastolic) - mm Hg	91 – 95	96 – 100	> 100	ER visit or hospitalization for malignant hypertension
Hypotension (systolic) - mm Hg	85 – 89	80 – 84	< 80	ER visit or hospitalization for hypotensive shock
Respiratory Rate - breaths per minute	17 – 20	21 – 25	> 25	Intubation

* Subject should be at rest for all vital sign measurements.

** Oral temperature, no recent hot or cold beverages or smoking.

*** When resting heart rate is between 60 – 100 beats per minute. Use clinical judgement when characterizing bradycardia among some healthy subject populations, for example, conditioned athletes.

Systemic (General)	Mild (Grade 1)	Moderate(Grade 2)	Severe (Grade 3)	Potentially Life Threatening (Grade 4)
Nausea/vomiting	No interference with activity or 1 – 2 episodes/24 hours	Some interference with activity or > 2 episodes/24 hours	Prevents daily activity, requires outpatient IV hydration	ER visit or hospitalization for hypotensive shock
Diarrhea	2 – 3 loose stools or < 400 gms/24 hours	4 – 5 stools or 400 – 800 gms/24 hours	6 or more watery stools or > 800gms/24 hours or requires outpatient IV hydration	ER visit or hospitalization

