10. PLANNED STATISTICAL METHODS

10.1. Statistical Considerations

10.1.1. General definitions

Definition of baseline

Baseline is defined as the last non-missing value for a participant, for the particular parameter, that is prior to the administration of study vaccine.

Study completion definition

A participant completes the study by engaging in study activities up to and including the End of Study Visit at Day 168 (+/- 7 days), for cohorts 1 to 4, and Day 84 (+/- 7 days) for cohorts 5 and 6.

Treatment Group

There are six treatment groups in this study; the Healthy Participants and CHB participants are split into high and low doses of vaccination. Healthy participants in the high dose group are further split into those with no previous exposure to ChAdOx1 vectored vaccines, those with recent previous exposure to Covid-19 ChAdOx1 vectored vaccine (cohort 5) and those with previous exposure to Covid-19 mRNA based vaccines (cohort 6).

Results below limit of detection and quantification

Immunogenicity results that are below the limit of quantification or detection (i.e. reported as <X or BLQ) will be replaced by 0 for any summaries but will be listed as reported.

Geometric Mean and Standard Deviation

The geometric mean (GM) and geometric standard deviation (GSD) are obtained by calculating the mean and SD of the log-transformed data and back-transforming these. If there are any zero values in the data a small number should be added to all values before log-transformation and then subtracted from the resulting GM. This small number will be 1 unless stated otherwise.

GM = antilog (mean (log(value + S))) – S, where S is a small number, relative to the non-zero results.

GSD = antilog(standard deviation(log(value + S)))

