10.8.4. Vital Signs

Vital signs parameters (temperature (C), pulse rate (bpm), systolic blood pressure (mmHg) and diastolic blood pressure (mmHg)) will be listed.

Toxicity grades will be calculated for relevant vital sign parameters, as per Appendix 1 of the study protocol (Section **Error! Reference source not found.**). Shift tables will be presented showing changes in each toxicity grade from the baseline grade to the maximum post-baseline grade for each treatment group.

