(2) The "Lab Parameter" is each of the haematology toxicity criteria in section **Error! Reference source not found.** Note, some laboratory parameters have 2 toxicity criteria (e.g. hyper and hypo)

Table 14.3.5
Shift Summary of Chemistry Results by Maximum Toxicity Grade
Safety Analysis Set

Use the same table shell as for Table 14.3.4, but apply chemistry toxicity criteria instead

Table 14.3.6
Shift Summary of Vital Signs Results by Maximum Toxicity Grade
Safety Analysis Set

Use the same table shell as for Table 14.3.4, but apply vital signs toxicity criteria instead
For temperature only use the temperature recorded as part of the vital signs assessments.

Listing 16.2.1.1
Participant Disposition

Cohort	Participant	Protocol Version	Informed Consent Date	CHB Diagnosis Date	Agreed to LFNA	Vaccination Date	Completed Study	Completion / Date (Study Day)	Reason for Withdrawal
xxxxxx	xxxxxx	ddmmmyyy	ddmmmyyy	ddmmmyyy	Yes/No	ddmmmyyy	Yes/No	ddmmmyyy	xxxxxxxxxx

CHB = Chronic Hepatitis B Virus Participant, HP = Healthy Participant, LFNA = Liver Fine Needle Aspirate.

Listing 16.2.1.2
Failed Inclusion and Exclusion Criteria

Cohort	Participant	Inclusion/Exclusion Criteria not met
xxxxxx	xxxxxx	xxxxxxxxxxxxxxxxxx

Programming note(s):

This listing is not required if no participants fail the criteria.

Listing 16.2.2
Protocol Deviations

Cohort	Participant	Deviations Reported	Date Reported	Start Date (Study Day)	End Date (Study Day)	Deviation Category [a]	Other Specify	Deviation Details/Comments	Major/Minor
xxxxxx	xxxxxx	Yes/No	ddmmyyyy	ddmmyyyy (xx)	ddmmyyyy (xx)	xx	xxxx	xxxxxx	Major/Minor

[1] Deviation categories: 1 = Informed consent procedure. 2 = Inclusion/exclusion criteria. 3 = Visit window. 4 = Study procedure / assessment performance. 5 = Concomitant Study procedure / assessment performance. 6 = Missing assessment / sample. 7 = Subject error. 8 = Investigational product. 9 = Concomitant medication / therapy. 10 = Other.

Listing 16.2.3
Analysis Sets

Cohort	Participant	Safety Analysis Set [1]	Per Protocol Analysis Set [2]	Immunogenicity Analysis Set [3]
xxxxxx	xxxxxx	Yes / No	Yes / No	Yes / No

[1] Safety Analysis Set = all participants who received a vaccination.

[2] Per Protocol (PP) Analysis Set = all participants in the safety analysis set who received the correct study vaccine and who had no major protocol deviations.

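### SAP Table 8 omits the protocol's resting-heart-rate condition on bradycardia grades, so Table 14.3.6 may show graded, and by chance worsened, bradycardia in participants with a naturally slow pulse

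*SAP*

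**What the plan says.** Protocol Appendix 1 has a vital-signs table with the row "Bradycardia - beats per minute": Grade 1 is 50 to 54, Grade 2 is 45 to 49, Grade 3 is below 45. The row carries a footnote with two parts. The first is a condition: "When resting heart rate is between 60 – 100 beats per minute". The second is a caution: "Use clinical judgement when characterizing bradycardia among some healthy subject populations, for example, conditioned athletes".

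SAP 15.2, Table 8, has the row "Bradycardia – beats per minute" with the same three cut-offs. It has no footnote, no condition and no caution.

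SAP 10.8.4 links the two: "Toxicity grades will be calculated for relevant vital sign parameters, as per Appendix 1 of the study protocol". The cross-reference that follows, to a section of the SAP, is broken. The same section sets the presentation: "Shift tables will be presented showing changes in each toxicity grade from the baseline grade to the maximum post-baseline grade for each treatment group". The shell for Table 14.3.6 says "Use the same table shell as for Table 14.3.4, but apply vital signs toxicity criteria instead" and adds nothing about heart rate. SAP 10.1.1 supplies the comparator: "Baseline is defined as the last non-missing value for a participant", taken before vaccination, which is a single reading.

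SAP section 11 lists two departures from the protocol analysis: fewer types of presentation for laboratory, vital-sign and physical-examination data, and a clarified per-protocol set. Neither concerns grading rules.

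**The concern.** The SAP names one scale as its source and prints a shortened form of it. A programmer working from Table 8 and the Table 14.3.6 shell would apply the cut-offs to every pulse reading. A participant whose pulse is usually in the low 50s would then carry a bradycardia grade that the protocol footnote appears intended to withhold.

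The shift layout does not fully correct this. One baseline reading is compared with the worst of several later readings, so ordinary variation tends to produce apparent worsening, especially in people whose usual pulse lies near the cut-offs.

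Among the planned tables in SAP 13.2, Table 14.3.6 is the only summary of pulse. The trial has no unvaccinated control, and groups have 5 to 15 participants, so one or two spurious shifts would be noticeable. There is also scope for mismatch in the study report. Protocol 8.2.1.1 says vital-sign abnormalities of Grade 3 or more are usually adverse events. A site that applies the footnote may report no event where Table 14.3.6 shows Grade 3.

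**Working it through.** **Side by side.** The cut-offs are identical in the two tables; the condition and the judgement clause appear only in the protocol. Conditional grading is not foreign to the SAP: its Table 3 grades bilirubin separately according to whether AST and ALT are normal or elevated.

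**What the condition must mean.** A reading of 54 or below cannot itself lie in 60 to 100. The footnote must therefore refer to another reading, presumably the person's usual or pre-vaccination rate. The protocol does not say which. Below I use the SAP baseline, as an assumption.

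**Table 8 applied literally.** 44 is Grade 3, 47 is Grade 2, 52 is Grade 1, and 57 and 62 are Grade 0. A slow pulse of 55 to 59 is ungraded until a reading falls to 54 or below.

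**Number of readings.** Scheduled post-dose pulse readings are Day 0 post-dose and Days 7, 14, 28, 56, 84 and 168 in cohorts 1 to 4 (7 readings, 5 + 5 + 6 + 6 = 22 participants). In cohorts 5 and 6, Days 56 and 168 drop out (5 readings, 30 participants).

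**Chance worsening for one person.** Assume independent normal readings around a usual pulse, rounded to whole beats. Let q₀ to q₃ be the probabilities that one reading is Grade 0 to 3, and Cᵢ = q₀ + … + qᵢ. With k post-dose readings,

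P(worst post-dose grade exceeds baseline grade) = Σ qᵢ(1 − Cᵢᵏ).

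Example: usual pulse 56, within-person SD 5, k = 7. Cutting at 54.5, 49.5 and 44.5 gives z = −0.3, −1.3, −2.3, so q = 0.618, 0.285, 0.086, 0.011. The sum is 0.618(1 − 0.618⁷) + 0.285(1 − 0.903⁷) + 0.086(1 − 0.989⁷) ≈ 0.597 + 0.145 + 0.006 = 0.75.

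Over within-person SD 3 to 5 and k = 5 or 7:

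| Usual pulse | P(worsened grade) |
|---|---|
| 53 | 0.58–0.76 |
| 56 | 0.60–0.75 |
| 65 | 0.00–0.12 |

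**Across participants.** The documents give no pulse mean or SD, so these inputs are assumed: mean 70, between-person SD 10, no vaccine effect, within-person SD 3, 5 or 7. Simulation with one baseline reading, 7 post-dose readings and the Table 8 cut-offs gives:

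| Within-person SD | Worsened grades with baseline below 60 | Grade 3 cases with baseline below 60 |
|---|---|---|
| 3 | 79% | about 100% |
| 5 | 55% | about 94% |
| 7 | 41% | 77% |

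At SD 5, about 17% of participants have a baseline below 60. With 7 readings 16% show a worsened grade and 3.7% reach Grade 3; with 5 readings the figures are 14% and 3.1%.

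Expected counts at SD 5:
- Worsened grade: 22 × 0.16 + 30 × 0.14 = 3.5 + 4.2 ≈ 8 of 52, about 4 of them with baseline below 60.
- Grade 3: 22 × 0.037 + 30 × 0.031 = 0.81 + 0.93 ≈ 1.7 of 52.

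**The case against.** The strongest reply is that the condition survives by reference. SAP 10.8.4 points to protocol Appendix 1, which contains the footnote, so a careful programmer could apply it. That stands: the documents show an inconsistency, not a settled decision to drop the condition. A reader might infer that slow-pulse participants will be counted as having bradycardia. The documents support only that they would be if Table 8 is programmed as printed.

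Second, the shift table already shows baseline grade. With mean 70, SD 5 and 7 readings, about 78% of participants reaching Grade 3 already carry a baseline grade of 1 or more (58% at SD 7). Most such cases would not look like new bradycardia from normal. This weakens the concern without removing it, since a chance move from Grade 1 to Grade 3 still reads as worsening.

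Third, a reader might infer that the protocol definitely leaves ungraded a fall from 56 to 53, or from 52 to 44. That depends on taking baseline as the resting heart rate, which the protocol does not state, and it sets aside the judgement clause.

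Fourth, the effect is small and descriptive. The counts spread over six groups, every reading is in Listing 16.2.9, and no safety testing is planned. The primary endpoints are adverse events, serious adverse events and Grade 3 or higher local and systemic reactions. Adverse-event severity is assessed by the investigator under Appendix 1, and pulse is not a solicited reaction. All of this stands.

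**Conclusion.** The omission is real and undeclared, and Table 8 conflicts with the scale SAP 10.8.4 says it follows. Programmed as printed, it would allow Grade 1 to 3 bradycardia, including chance worsening, in participants with a naturally slow pulse. Under the assumed inputs this means about 8 of 52 participants with a worsened grade at within-person SD 5, roughly half of them with baseline below 60.

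It is tempting to say that most worsened grades, and nearly all Grade 3 results, would come from people who were already slow. That is not robust: at within-person SD 7 the shares fall to 41% and 77%. These figures also rest on an assumed mean, assumed SDs, independent readings and baseline as the qualifying rate. Only Table 14.3.6 and the grades in Listing 16.2.9 are affected; the primary endpoints are not. It merits correction as an inexpensive inconsistency in a safety summary.

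**What to change.** - Restore the footnote condition in SAP Table 8 and in Table 14.3.6.
- State which pre-vaccination reading defines resting heart rate, for example the SAP baseline, and say how the clinical-judgement clause is handled, since a judgement cannot be calculated.
- Repair the broken cross-reference in SAP 10.8.4.
- In Table 14.3.6, show participants with baseline pulse below 60 in a separate row, with their lowest post-dose pulse or change from baseline, so that a real fall stays visible in the summary and not only in the listing.

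If the sponsor prefers unconditional cut-offs, SAP section 11 should declare that as a change from the protocol.

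The cost is a footnote, one programming condition and one extra row. The downside is small: participants with baseline below 60 no longer carry a toxicity grade for bradycardia, and a hard cut on one noisy reading will misclassify some people near 60.
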